Five colonoscopists with experience in WE performed WECAC at 3 sites (47) (Table 5, A). In 45 male patients completing without sedation, the low mean RTMIP of WECAC observed in a published pilot study (11) was reproduced (Table 5, A vs. B). In U.S. cohorts, mean RTMIP of WECAC was lower than those of historical unsedated cohorts examined by WE (5,6) (Table 5, A vs. C-D, respectively).

	Table 5: Comparison of real-time maximum insertion pain (RTMIP)						
Technique I		References	Study Sites	No. of Investigators (type of no sedation)	RTMIP		
Α	A WECAC 47		2 U.S., 1 Taiwan	5 (mixed on demand & scheduled unsedated)	1.5 (1.8)		
B WECAC		11	1 U.S.	3 (Scheduled unsedated)	1.2 (1.5)		
С	WE	5	1 U.S.	1 (Scheduled unsedated)	3.6 (2.1)*		
D	WE	6	1 U.S.	2 (Scheduled unsedated)	3 (3.0)*		

Frequency; mean (SD). A=unpublished preliminary; B=published pilot; RTMIP, real-time maximum insertion pain; VAS: 0=none, 10=most severe., *p < 0.05, vs. 1.5 (1.8), t test.

Table 6 shows comparable intubation rates. Trends favored WECAC in intubation time WECAC (18-20 min) vs. WE (13-34 min), right colon preparation WECAC (3.1-3.3) vs. WE (2.3-3.0), painless insertion WECAC (41-51%) vs. WE (10-28%); overall ADR (56% vs. 46%), and proximal colon ADR (46% vs. 40%).

	Table 6: Demographics and procedural outcomes										
Tec	hnique	n	Age (yrs)	BMI	PAS	PAS Cecal Intubation		Proximal Bowel	Painless	Overall ADR	Proximal
100	imique	''	Age (yrs)	DIVII	Yes Time Rate (%)		Prep Score	insertion	Overall ADIC	Colon ADR	
Α	WECAC	45	62 (10)	29 (4)	34%	20 (14)	96	3.1 (0.5)	51%	Combined	Combined
В	WECAC	26	64 (8)	31 (5)	1	18 (12)	96	3.3 (0.5)	41%	40/72 (56%)	33/72 (46%)
С	WE	42	66 (9)	32 (7)	1	34 (3)	97.6	3.0 (0.7)	10%	Combined	Combined
D	WE	50	61 (7)	30 (7)	30%	13 (7)	96	2.3 (0.5)	28%	42/92 (46%)	37/92 (40%)
DΛG	nrior and	omina	l curgary	Rowel	nran co	ore: 1-e	vcallant: 3	2- annd: 2- fair: 1	- noor Da	ta maan (SD)	· % total

PAS, prior abdominal surgery. Bowel prep score: 4=excellent; 3= good; 2= fair; 1= poor. Data, mean (SD); % total.

	Table 7: Procedural details					
Technique	Screening/	Position Change (%)	Abdominal	Water Volume on	Withdrawal	
recillique	Surveillance/	Position Change (70)	Compression (%)	Arrival to Cecum (L)	Time (min)	

		Diagnostic	Yes	Combined	Yes	Combined	Infused	Suctioned	
Α	WECAC	19/15/11	29	25%	44		1.6 (0.8)	1.9 (1.4)	21 (11)
В	WECAC	17/10/0	19	25%	30		1.3 (1.2)	1.4 (1.6)	23 (13)
С	WE	17/17/8	64	34%	57	400/	1.8 (0.7)		22 (13)

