Method of randomization. After signing informed consent patients will be randomized to WE or WECAC, based on computer generated random numbers accessible using the web-based randomization application set up by the Data Curation Center (DCC) programmer. The code will be revealed when the colonoscopist is ready to insert the endoscope to begin the examination. Randomization will be carried out by the method of random permuted block design with variable block sizes of 4 and 6. Gender will be used as a stratification factor. The 7 VA investigators will be a blocking factor for the randomization to obtain treatment balance across investigators, however in the analytical phase the data from these investigators will be combined for the analysis of the primary endpoint.

Control technique (WE) (Table 8). (5,8,9,23,41) Complete exclusion of air (air pump off) minimizes colon distention and elongation. Water will be infused via the accessory channel intermittently during insertion using a peristaltic pump. Turbid water due to residual feces will be suctioned and replaced by clean water to ensure visualization of the lumen. Suction of infused water and all residual air will be implemented. Infused water will be removed predominantly during insertion (checked by the volume infused and suctioned being comparable upon arrival to the cecum). Adjunct maneuvers will be used as described later. Cecal intubation is confirmed by touching the floor of the cecum, and viewing the medial aspect of the cecum between the appendix orifice and ileocecal valve. Mucosal inspection, biopsy or polypectomy will be performed in the air filled colon during withdrawal using withdrawal time >6 min.

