Updated male Veteran sample size. Pilot data in scheduled unsedated male Veterans were updated. The real time maximum insertion pain (RTMIP) [mean (SD)] was 2.7 (2.2) with WE (n=87) and 1.5 (2.1) with WECAC (n=38). The reduction (44%) 2.7-1.5=1.2 is 1.2/2.2=0.55 standard deviation (SD) units. The sample size/group needed to detect a difference at a level of significance of 0.0492 (adjusted for Obrien-Fleming interim stopping rules, one interim analysis at 50% completion) with 90% power is 72 or 144 total using a twosided two sample t-test. Assuming 90% of subjects will be evaluable, we plan to recruit 160 male Veterans. Updated pilot data showed the PI performed 30 scheduled unsedated colonoscopies (male) in 1 year when ~2200 colonoscopies were offered at VAGLAHS (1.36%). At participating sites, a total of ~9000 colonoscopies (VAGLAHS 2200, VANCHCS 3300, VAPAHCS 3500) will be performed each year. For purpose of conservative estimation, 1/2 of 1.36% (0.68%) of all colonoscopies will be presumed to be in scheduled unsedated male Veterans when the option is made available up front. In 51 month (4.25 year) enrollment period, a total of 38250 colonoscopies will be performed. 260 (0.68% of 38250) male Veterans will receive scheduled unsedated colonoscopy, making target enrollment of 160 achievable (only 160/260 = 62% enrollment rate needed). In support of this possibility, in two prior RCT in scheduled unsedated male Veterans at VAGLAHS and VANCHCS comparing WE vs. air colonoscopy, high enrollment rates of 97.7% (84/86) and 95.2% (100/105), respectively, were recorded. Sample size of 160 will be sufficient to show significant differences in some of the previously listed secondary outcomes related to quality colonoscopy in

Secondary outcome power estimates based pilot data in WE (n=87) and WECAC (n=38) in male Veterans					
Secondary Outcomes	Pilot (WE vs. WECAC)	Difference (SDU or %)	Sample size per group needed*		
Recalled pain, score (SD)	1.5(2) vs. 0.5(2)	1 (0.5 SDU)	84 (Will be dropped)		
Successful cecal Intubation	98% vs. 100%	2%	(Will be dropped)		
Proportion with no pain	18% vs. 46%	28%	54		
Insertion time, minutes (SD)	15(5) vs. 12( 5)	-3 (0.6 SDU)	58		
Overall ADR - entire colon	36% vs. 50%	14%	258		
Proximal colon ADR	17% vs. 40%	23%	76		
Right colon ADR	20% vs. 40%	20%	106		
Willing to repeat, score (SD)	9.0(2.5) vs. 9.6(0.9)	0.6 (0.4 SDU)	(Will be dropped)		

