ADR, adenoma detection rate; SD, standard deviation; U, units. *90% power, 95% confidence or 5% α error level.					

male Veterans (e.g. proportion with no pain, insertion time, proximal colon ADR). The remaining previously listed secondary outcomes in male Veterans will be dropped (e.g. recalled pain, successful cecal intubation, overall and right colon ADR, willing to repeat).

Updated female Veteran sample size. After receipt of the critique, the PI identified 9 scheduled unsedated female Veterans (5 WE, 4 WECAC). RTMIP were WE, 6.2 (3.5) and WECAC, 3.5 (3.7). The reduction (44%) was 2.7/3.7 or 0.7 SD unit. The female Veterans had significantly higher RTMIP than the male Veterans when examined by WE, but the percent reduction of RTMIP by WECAC was equivalent (44%). The sample size/group needed to detect a difference at a level of significance of 0.0492 (adjusted for Obrien-Fleming interim stopping rules, one interim analysis at 50% completion) with 90% power is 43 or 86 total using a two-sided two sample t-test. Assuming 90% of subjects will be evaluable, we plan to recruit 96 female Veterans. Sample size of 96 will be sufficient to show significance in differences in some of the previously listed secondary outcomes related to quality colonoscopy in female Veterans (e.g. proportion with no pain, insertion time, overall and segmental ADR). The remaining previously listed secondary outcomes in female Veterans will be dropped (e.g. recalled pain, successful cecal intubation, willing to repeat).

Secondary outcome power estimates based pilot data in WE (n=5) and WECAC (n=4) in female Veterans					
Secondary Outcomes	Pilot (WE vs. WECAC)	Difference (SDU or %)	Sample size per group needed*		
Recalled pain, score (SD)	3.1(3) vs. 1.6(3)	1.5 (0.5 SDU)	84 (Will be dropped)		
Successful cecal Intubation	100% vs. 100%	0%	(Will be dropped)		
Proportion with no pain	0% vs. 25%	25%	32		
Insertion time, minutes (SD)	17(4.5) vs. 14(4.5)	-3 (0.7 SDU)	43		
Overall ADR - entire colon	20% vs. 50%	30%	48		
Proximal colon ADR	20% vs. 50%	30%	48		
Right colon ADR	20% vs. 50%	30%	48		
Willing to repeat, score (SD)	9.2(1.1) vs. 9.5(1.0)	0.3 (0.3 SDU)	233 (Will be dropped)		
ADR, adenoma detection rate; SD, standard deviation; U, units. *90% power, 95% confidence or 5% $\alpha$ error level.					

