Primary hypothesis. Real-time maximum insertion pain (RTMIP) is significantly lower in the patients examined by the WECAC technique compared with the WE technique. The analysis will compare 2 groups (WECAC vs. WE) with a two sample t-test. If the data show substantial non-normality (as in a prior dataset with WE (5)); we will compare the groups with a Mann-Whitney *U* test; P<0.0492 considered significant. Secondary analysis of the primary outcome will utilize mixed effects regression models to evaluate the effects of potential covariates/confounds described in Tables 9 and 10. First, we will assess the effect of each individual covariate in regression models including the effect for group assignment and gender (stratification factor in the randomization), as well as the covariate by group interaction. Next, we will construct a multiple regression model with the set of covariates found to be significant (either as a main effect or an interaction effect) in an overall regression model along with group assignment.

Dependent Variables	Variable Type	Analysis method
Primary Outcome		
RTMIP (0=none,	Continuous	2 sample Student t test. However, if distribution of the data is skewed as
10=most severe)	Continuous	seen in an earlier study (5), the Mann-Whitney U test will be used.

We have updated the analytic plan to include multi-level random effects (hierarchical model) for study site and provider within site. We will include two levels of random effects in this model: 1. random effects for study site, 2. random effects for provider which will be nested within sites.

Secondary hypotheses. WECAC produces significantly higher quality colonoscopy outcomes. For example, when WE alone and WECAC are compared, the proportion completing colonoscopy with no pain, insertion time, and ADR in the proximal colon will be significantly different. For continuous secondary outcomes (e.g. insertion time), we will use a similar analysis strategy as that used for the primary outcome. For dichotomous secondary outcomes (e.g., no pain, proximal colon ADR) we will use Chi-square tests to compare the outcomes between the groups. Generalized logistic models will be used to adjust for covariates, gender and study site for these outcomes.

Dependent Variables	Variable Type	Analysis method
Insertion time	Continuous	Student t test
No insertion pain (yes, no); proximal colon adenoma detection (yes, no)	Binary	Chi square

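### Allocation is balanced by investigator and gender, but the headline tests carry neither factor and the models that do have a secondary or undefined role; the tests err on the conservative side and can lose power

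*Protocol*

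**What the plan says.** Protocol, section (4)(b), Method of randomization: permuted blocks of 4 and 6, gender as a stratification factor and the seven investigators as a blocking factor. It adds that "in the analytical phase the data from these investigators will be combined for the analysis of the primary endpoint".

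SAP, Primary hypothesis: "The analysis will compare 2 groups (WECAC vs. WE) with a two sample t-test", with a Mann-Whitney test if the data are clearly non-normal. The 0.0492 threshold is attached to this comparison. Mixed-effects regression with group and gender follows, labelled a secondary analysis of the primary outcome. A later paragraph adds random effects for site and for provider within site, without saying whether that model decides the primary question or supports it.

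SAP, Secondary hypotheses: "For continuous secondary outcomes (e.g. insertion time), we will use a similar analysis strategy as that used for the primary outcome"; the accompanying table lists a Student t-test for insertion time and chi-square for no insertion pain and proximal colon adenoma detection. Logistic models with gender and site are planned for the binary outcomes as an adjustment step.

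Two related points are unsettled. The sample sizes are sex-specific (144 evaluable men, 86 evaluable women), while the Primary hypothesis paragraph describes a single two-group comparison. And the Introduction of the abbreviated protocol names investigator and type of colonoscopy as stratifiers within site, with no mention of gender.

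**The concern.** Balancing the arms within investigator and gender removes differences between those strata from the arm comparison. An unadjusted test still counts them as noise, so its standard error is larger than the true one. The test then rejects less often than its nominal level under the null and less often than it could when there is an effect.

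There is reason to expect such differences. The pilot RTMIP means under WE are far apart by sex: in men RTMIP "was 2.7 (2.2) with WE (n=87) and 1.5 (2.1) with WECAC (n=38"), while in women "RTMIP were WE, 6.2 (3.5) and WECAC, 3.5 (3.7"). For insertion time the Protocol reports "Trends favored WECAC in intubation time WECAC (18-20 min) vs. WE (13-34 min"), the WE range coming from two earlier cohorts at 34 (3) and 13 (7) minutes. The trial also deliberately uses investigators with differing experience. At stake are efficiency and clarity about which analysis decides the primary question.

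**Working it through.** **The plan's own figures.** With z = 1.967 for two-sided 0.0492 and 1.282 for 90% power:
- Men: 2 × ((1.967 + 1.282) × 2.2/1.2)² = 70.9; the t-based formula gives 71.9. This matches the SAP's 72 per group ("with 90% power is 72 or 144 total using a twosided two sample t-test"). 144/0.9 = 160.
- Women, 0.7 SD: 43.1 by the normal formula, 44.1 by t, against 43 stated. 86/0.9 = 95.6, so 96.
- Insertion time in men, 0.6 SD at 0.05: 58.4, against 58 stated.

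The sample sizes reproduce to within two patients per group.

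**Method.** Let W be the within-stratum variance, B the between-stratum variance and N the evaluable total, split 1:1. With balanced strata the true standard error of the arm difference is S = √(4W/N). The unadjusted test uses U = √(4(W+B)/N). Then, approximately:
- unadjusted type I error = 2 × [1 − Φ(z·U/S)]
- unadjusted power = Φ((δ − z·U)/S)
- adjusted power = Φ(δ/S − z)

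Simulations with blocks of 4 and 6 within strata were also run; they differ slightly because blocks do not balance perfectly. Normal outcomes and an even spread of patients over seven operators are assumptions.

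**RTMIP, sexes pooled** (N = 230; SDs 2.2 and 3.5; WE means 2.7 and 6.2):
- W = (144 × 2.2² + 86 × 3.5²)/230 = 7.61
- B = (144 × 86/230²) × 3.5² = 2.87, about 27% of the total
- S = 0.364, U = 0.427
- Type I error = 2 × [1 − Φ(1.967 × 0.427/0.364)] = 2.1%. Simulations gave 2.1% to 2.7%, centred near 2.3%. If the sex gap is 2.75 (the average over both arms), it is about 3%.
- Power for a common 1.2-point effect: Φ((1.2 − 0.840)/0.364) = 84% unadjusted, Φ(3.30 − 1.967) = 91% adjusted; simulated about 83% and 90%.
- At the planned effects (1.2 in men, 2.7 in women): simulated 99.7% and 99.9%.

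**RTMIP, each sex tested separately.** The documented WE means at two sites are 3.6 (2.1), n = 42, and 3 (3), n = 50. The gap is 0.6 with SE √(2.1²/42 + 3²/50) = 0.53, so z = 1.12 and p = 0.26; it explains about 1.3% of variance. With that gap, simulated type I error is 4.8% in men and 4.7% in women. Power, unadjusted against adjusted, is 89.8% against 90.0% in men and 91% against 91% in women.

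**Insertion time** (144 men, 3-minute effect, two-sided 0.05):

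| Case | W | B | Unadjusted power | Adjusted power |
|---|---|---|---|---|
| Within-operator SD 5, operator SD 3 (assumed) | 25 | 9 | 91% (simulated 90%) | 95% |
| Within-operator SD 5, operator SD 5 (assumed) | 25 | 25 | 80% (simulated 79%) | 95% |
| Total SD 5, of which operator SD 3 (assumed) | 16 | 9 | 98% | 99% |
| Table 6 at face value: half the operators 34 (3), half 13 (7) | 29 | 110 | 17% | 92% (simulated 91%) |

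For the first row: S = √(100/144) = 0.833, U = √(136/144) = 0.972, power = Φ((3 − 1.905)/0.833) = 91%; type I error is 2.2%.

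The last row is a worst-case bound. Pooling the two cohorts gives (42 × 34 + 50 × 13)/92 = 22.6 minutes with SD 11.8, which does not fit the SAP pilot value of 15 (5) for WE. The cohorts had one and two investigators, so site, operator and period are confounded.

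**The case against.** The strongest reply is that the plan does not ignore these factors. Gender is in the mixed model, site and provider within site are in the hierarchical model, and gender and site are in the logistic models. The sentence about combining investigators could mean only that no per-investigator results will be reported. All of this stands, and it confines the point to which analysis is the headline one. It does not remove the point, because the threshold is attached to the unadjusted comparison and no text promotes a model over it.

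Three stronger readings are tempting, and the documents do not support them.
- A reader might infer that the trial risks a spurious positive. The error runs the other way in every case computed.
- A reader might carry the wide differences between the earlier cohorts over to the primary endpoint. They concern insertion time, painless insertion (10% against 28%) and position change (64% against 8%); RTMIP under WE hardly differs (3.6 against 3.0).
- A reader might conclude that the trial is underpowered. The planning SDs are raw within-arm pilot SDs, which may already contain operator variation. With total SD held at 2.2 and an assumed operator SD of 1.0, simulated power in men is about 93% unadjusted and 95% adjusted.

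The plan also standardises technique across sites, which should narrow operator differences.

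**Conclusion.** The point holds as one of efficiency and specification. The designated tests omit the factors used to balance allocation, and the adjusted models are secondary or undefined in role.

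For RTMIP the consequence is material only if the sexes are pooled: a test run at about 2.3% instead of 4.92%, and about 7 points of power lost at a common 1.2-point effect. It rests on the pilot sex gap, and the female pilot has only nine patients. With sex-specific testing it is negligible at the documented site gap; operator SDs above that are assumptions (at 1.5, added to a within-operator SD of 2.2, simulated power in men is 81% against about 90%).

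For insertion time the loss ranges from nothing of consequence to about 16 points at an assumed operator SD of 5 minutes, depending on whether the SAP's SD of 5 is a within-operator or a total SD, which the documents do not say. The simulations used normal outcomes although the pain scale is bounded and may be skewed; the Mann-Whitney test behaved similarly in the pooled case (about 2%). The change is worth making because it costs almost nothing.

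**What to change.** In the Protocol's Method of randomization and the SAP's Primary and Secondary hypotheses:

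1. Reconcile the stratifiers first: investigator and type of colonoscopy (abbreviated protocol) against gender and investigator (detailed protocol). The model should follow whatever the randomisation system uses.
2. State whether RTMIP is tested within each sex or pooled.
3. Make the headline analysis of RTMIP and insertion time a pre-specified model with arm, investigator (fixed effects, or the provider-within-site random effects already planned) and, where the sexes are analysed together, gender. If a rank test is needed, use the van Elteren test on the same strata.
4. For no pain and proximal ADR, make the planned logistic model with gender and site the headline analysis, or use a Cochran-Mantel-Haenszel test on coarse strata such as site by gender. Investigator by gender would be sparse: 86/7 is about 12 women per investigator, or six per arm.
5. Keep the unadjusted tests as supporting analyses, and replace the sentence combining investigators with one naming the adjusted model.

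Cost: wording, and six or seven degrees of freedom if investigator is fixed (six for seven investigators, one for gender). No extra patients or data are needed, since investigator and gender are recorded anyway.

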## General analytic plan (data management plan, sample size calculations, statistical analysis):

Data management plan. During the planning and start-up period, all elements of an accurate, reliable, and efficient data management plan will be developed by the Data Curation Center (DCC). The database programmer, in close collaboration with the cross-functional DCC team and with input from the investigators, will build the study-specific data collection application and database. OpenClinica® [www.openclinica.org] is a clinical trial software platform for electronic data capture, clinical data management, and clinical monitoring that is a 21 CFR Part 11 compliant system, using Oracle® as the relational database back-end. We will build the infrastructure necessary to input research data into the Oracle® databases using a web-based data entry system that incorporates front-end edit checks (e.g., data range and logical checks) to ensure that data are entered completely and correctly. Additionally, the DCC data manager and site study coordinators will develop a plan to identify and resolve back-end data errors. The enhanced discrepancy management function in OpenClinica® will expedite query resolution by allowing electronic communication of discrepancy reports between the UCLA DCC and site coordinators. The DCC programmer will develop the web-based randomization application. The DCC will develop consistency checks; both within patients across study visits and between sites. The clinical monitoring and data management procedures will be consistent with the International Conference on Harmonization (ICH E6) standards for Good Clinical Practice. Quality assurance will be accomplished in part by monthly data monitoring reports that will be discussed during meetings of the Steering Committee (PD/PI, site PIs and statistics consultant).

Sample size determination and description of subject population.

Updated male Veteran sample size. Pilot data in scheduled unsedated male Veterans were updated. The real time maximum insertion pain (RTMIP) [mean (SD)] was 2.7 (2.2) with WE (n=87) and 1.5 (2.1) with WECAC (n=38). The reduction (44%) 2.7-1.5=1.2 is 1.2/2.2=0.55 standard deviation (SD) units. The sample size/group needed to detect a difference at a level of significance of 0.0492 (adjusted for Obrien-Fleming interim stopping rules, one interim analysis at 50% completion) with 90% power is 72 or 144 total using a twosided two sample t-test. Assuming 90% of subjects will be evaluable, we plan to recruit 160 male Veterans. Updated pilot data showed the PI performed 30 scheduled unsedated colonoscopies (male) in 1 year when ~2200 colonoscopies were offered at VAGLAHS (1.36%). At participating sites, a total of ~9000 colonoscopies (VAGLAHS 2200, VANCHCS 3300, VAPAHCS 3500) will be performed each year. For purpose of conservative estimation, 1/2 of 1.36% (0.68%) of all colonoscopies will be presumed to be in scheduled unsedated male Veterans when the option is made available up front. In 51 month (4.25 year) enrollment period, a total of 38250 colonoscopies will be performed. 260 (0.68% of 38250) male Veterans will receive scheduled unsedated colonoscopy, making target enrollment of 160 achievable (only 160/260 = 62% enrollment rate needed). In support of this possibility, in two prior RCT in scheduled unsedated male Veterans at VAGLAHS and VANCHCS comparing WE vs. air colonoscopy, high enrollment rates of 97.7% (84/86) and 95.2% (100/105), respectively, were recorded. Sample size of 160 will be sufficient to show significant differences in some of the previously listed secondary outcomes related to quality colonoscopy in

Secondary outcome power estimates based pilot data in WE (n=87) and WECAC (n=38) in male Veterans					
Secondary Outcomes	Pilot (WE vs. WECAC)	Difference (SDU or %)	Sample size per group needed*		
Recalled pain, score (SD)	1.5(2) vs. 0.5(2)	1 (0.5 SDU)	84 (Will be dropped)		
Successful cecal Intubation	98% vs. 100%	2%	(Will be dropped)		
Proportion with no pain	18% vs. 46%	28%	54		
Insertion time, minutes (SD)	15(5) vs. 12( 5)	-3 (0.6 SDU)	58		
Overall ADR - entire colon	36% vs. 50%	14%	258		
Proximal colon ADR	17% vs. 40%	23%	76		
Right colon ADR	20% vs. 40%	20%	106		
Willing to repeat, score (SD)	9.0(2.5) vs. 9.6(0.9)	0.6 (0.4 SDU)	(Will be dropped)		
ADR, adenoma detection rate; SD, standard deviation; U, units. *90% power, 95% confidence or 5% α error level.					

male Veterans (e.g. proportion with no pain, insertion time, proximal colon ADR). The remaining previously listed secondary outcomes in male Veterans will be dropped (e.g. recalled pain, successful cecal intubation, overall and right colon ADR, willing to repeat).

Updated female Veteran sample size. After receipt of the critique, the PI identified 9 scheduled unsedated female Veterans (5 WE, 4 WECAC). RTMIP were WE, 6.2 (3.5) and WECAC, 3.5 (3.7). The reduction (44%) was 2.7/3.7 or 0.7 SD unit. The female Veterans had significantly higher RTMIP than the male Veterans when examined by WE, but the percent reduction of RTMIP by WECAC was equivalent (44%). The sample size/group needed to detect a difference at a level of significance of 0.0492 (adjusted for Obrien-Fleming interim stopping rules, one interim analysis at 50% completion) with 90% power is 43 or 86 total using a two-sided two sample t-test. Assuming 90% of subjects will be evaluable, we plan to recruit 96 female Veterans. Sample size of 96 will be sufficient to show significance in differences in some of the previously listed secondary outcomes related to quality colonoscopy in female Veterans (e.g. proportion with no pain, insertion time, overall and segmental ADR). The remaining previously listed secondary outcomes in female Veterans will be dropped (e.g. recalled pain, successful cecal intubation, willing to repeat).

Secondary outcome power estimates based pilot data in WE (n=5) and WECAC (n=4) in female Veterans					
Secondary Outcomes	Pilot (WE vs. WECAC)	Difference (SDU or %)	Sample size per group needed*		
Recalled pain, score (SD)	3.1(3) vs. 1.6(3)	1.5 (0.5 SDU)	84 (Will be dropped)		
Successful cecal Intubation	100% vs. 100%	0%	(Will be dropped)		
Proportion with no pain	0% vs. 25%	25%	32		
Insertion time, minutes (SD)	17(4.5) vs. 14(4.5)	-3 (0.7 SDU)	43		
Overall ADR - entire colon	20% vs. 50%	30%	48		
Proximal colon ADR	20% vs. 50%	30%	48		
Right colon ADR	20% vs. 50%	30%	48		
Willing to repeat, score (SD)	9.2(1.1) vs. 9.5(1.0)	0.3 (0.3 SDU)	233 (Will be dropped)		
ADR, adenoma detection rate; SD, standard deviation; U, units. *90% power, 95% confidence or 5% $\alpha$ error level.					

In both male and female Veterans, record will be kept of all these variables, however, to demonstrate comparability of the study and control groups. When the male and female data are combined, the sample size may reveal differences between WE and WECAC that are worth pursuing, thus providing pilot data for future studies (e.g. overall and segmental adenoma detection rates in scheduled unsedated subjects).

Statistical Analysis. Analysis will be performed based on assigned groups using STATA software (StataCorp 2013. Stata Statistical Software. College Station, TX: StataCorp LP). Descriptive statistics (frequencies, measures of central tendency and dispersion) will be used to evaluate the distribution of each variable. Data as mean (SD) or median (IQR) will be assessed by 2-samples independent samples tests (e.g. Student's t), Fisher exact test; relative risk tests and correlation analysis will be used to evaluate hypotheses. P<0.05 will be considered significant. Statistical assumptions required will be checked and appropriate data transformations or non-parametric test (e.g. Wilcoxon-Mann-Whitney *U test*,) will be used if assumptions are not met. Linear regression will be used to determine significant factor(s) that impact on the primary outcome. The analysis will use intention-to-treat principles, i.e., all randomized patients will be included in the analysis even if their colonoscopies were discontinued early (e.g., pain, poor preparation). The pain score at discontinuation will be used for the analysis for patients with early discontinuation.

Hypotheses Testing. There will be one-interim analysis and a final analysis for this study. The interim analysis will be conducted after 50% of subjects have been evaluated. This interim analysis will be for the primary analysis alone. The significance level for the interim analysis will be 0.0054 based on the standard O'Brien-Flemming rule. The study will be stopped if there is a significant result for the interim analysis. The final analysis will use a 0.0492 level of significance.

Primary hypothesis. Real-time maximum insertion pain (RTMIP) is significantly lower in the patients examined by the WECAC technique compared with the WE technique. The analysis will compare 2 groups (WECAC vs. WE) with a two sample t-test. If the data show substantial non-normality (as in a prior dataset with WE (5)); we will compare the groups with a Mann-Whitney *U* test; P<0.0492 considered significant. Secondary analysis of the primary outcome will utilize mixed effects regression models to evaluate the effects of potential covariates/confounds described in Tables 9 and 10. First, we will assess the effect of each individual covariate in regression models including the effect for group assignment and gender (stratification factor in the randomization), as well as the covariate by group interaction. Next, we will construct a multiple regression model with the set of covariates found to be significant (either as a main effect or an interaction effect) in an overall regression model along with group assignment.

Dependent Variables	Variable Type	Analysis method
Primary Outcome		
RTMIP (0=none,	Continuous	2 sample Student t test. However, if distribution of the data is skewed as
10=most severe)	Continuous	seen in an earlier study (5), the Mann-Whitney U test will be used.

We have updated the analytic plan to include multi-level random effects (hierarchical model) for study site and provider within site. We will include two levels of random effects in this model: 1. random effects for study site, 2. random effects for provider which will be nested within sites.

Secondary hypotheses. WECAC produces significantly higher quality colonoscopy outcomes. For example, when WE alone and WECAC are compared, the proportion completing colonoscopy with no pain, insertion time, and ADR in the proximal colon will be significantly different. For continuous secondary outcomes (e.g. insertion time), we will use a similar analysis strategy as that used for the primary outcome. For dichotomous secondary outcomes (e.g., no pain, proximal colon ADR) we will use Chi-square tests to compare the outcomes between the groups. Generalized logistic models will be used to adjust for covariates, gender and study site for these outcomes.

Dependent Variables	Variable Type	Analysis method
Insertion time	Continuous	Student t test
No insertion pain (yes, no); proximal colon adenoma detection (yes, no)	Binary	Chi square

Exploratory hypotheses. Co-variables affect patients' report of RTMIP. Patient-related factors include age, gender, ethnicity, education, BMI, indication for colonoscopy, current symptomatic hemorrhoids,

Dependent Variables	Variable	Analysis method		
Primary Outcome				
RTMIP	Continuous	Mixed effects regression, predict lower insertion pain, predictors-covariables		
Co-variables			Variable	Analysis method
Recalled maximum inse	Recalled maximum insertion pain score (blinded) [validates primary]			Correlate RTMIP
Body mass index (yes, no)			Continuous	
Age (<40 years) (yes, no); gender (male, female); ethnicity (White, Black, Hispanic, Asian, other) (yes, no); indication (Screening, surveillance, diagnostic); hemorrhoids (yes, no); chronic pain treatments (yes, no); substance abuse (yes, no); prior abdominal surgery (yes, no), sedation colonoscopy (yes, no), unsedated colonoscopy (yes, no), painful colonoscopy (yes, no); diverticulitis (yes, no); indication (abdominal pain) (yes, no); anticipation of pain (yes, no);  Exploratory variables			Binary	
Staff satisfaction (0=not satisfied to 10=very satisfied)			Continuous	
Adequacy of patient blinding (yes, no); Loop reduction maneuvers (yes, no); Position change (yes, no); Abdominal compression (yes, no); Need to change technique (yes, no); Failed (poor prep) (yes, no); Pain tolerance (patient reported) (0=low, 1=high); Reason for unsedated (no ride, personal preference, other) (yes, no); Previous endoscopy experience (0=not good, 1=good); Objective anxiety (0=none, 1=high) (by endoscopist before examination); overall adenoma detection - entire colon (yes, no);			Binary	

chronic pain treatment, substance abuse, prior abdominal surgery, prior colonoscopy with or without sedation, current abdominal discomfort, expectation on day of colonoscopy, patient reported pain tolerance and subjective anxiety, objective anxiety assessed by colonoscopist, and reason for choice of no sedation. Procedure-related factors include technique of insertion, use of loop reduction maneuvers by the colonoscopist, change of patient position, application of abdominal compression by the assistant and insertion time, and length of colonoscope needed to reach the cecum. Examples: patients are more likely to report higher RTMIP amongst those with younger age, longer duration of insertion, lower expectation of painless insertion, female gender, low BMI, more frequent need for position change or abdominal compression. More patients will report lower RTMIP if there is low patient anxiety, good expectation of today's examination, no

prior abdominal surgery, colonoscopist use loop reduction maneuvers. The analysis of the exploratory outcomes will follow the same structure as the primary and secondary outcomes. To control for the multiplicity of exploratory outcomes we use the false-discovery rate (FDR) of Benjamini and Hochberg (67) rather than the traditional Bonferroni adjustment. The FDR assesses estimates the proportion of significant findings that are false positive results. The FDR method is less conservative and better preserves our ability to detect differences between groups.

Interim analysis. After 50% of subjects complete the protocol and data collection we will perform an inferential analysis of the primary endpoint as described in the statistical methods section. The only difference between the interim analysis of the primary endpoint and the final analysis will be the level of significance of the tests. If there is a significant treatment effect, this would communicated to the study Data and Safety Monitoring Board (DSMB) to consider early termination for efficacy.

Safety and Monitoring. This study has MODERATE risk with the potential of uncommon serious adverse events or unanticipated problems involving risks to participants. The local site investigator will be responsible for following adverse event (AE) reporting requirements: a. Reviewing the accuracy and completeness of all AEs reported; b. Complying with study policies as well as local IRB policies for reporting adverse medical events (AMEs) and/or serious adverse events (SAEs); c. Reporting to the IRB safety issues reported to the site by the sponsor (PI), and; d. Closely monitoring research volunteers for any new AMEs or SAEs. An AME is defined as "any untoward medical occurrence in a patient or clinical investigation subject administered a pharmacological product which does not necessarily have to have a causal relationship with this treatment". An AME can therefore be any unfavorable or unintended sign (including an abnormal laboratory finding), symptom, or disease temporally associated with the study intervention. All AMEs with a reasonable causal relationship to the investigative treatment will be considered at least "possibly related". A definite relationship does not need to be established. SAEs are a subset of AMEs defined by the International Conference on Harmonization for Clinical Safety Data Management as untoward medical occurrences that at any dose; a. Result in death; b. Are life-threatening; c. Require inpatient hospitalization or prolongation of existing hospitalization; d. Result in persistent or significant disability or incapacity; e. Result in a congenital anomaly/birth defect; or f. Result in any other condition that, based upon medical judgment, may jeopardize the subject and require medical or surgical treatment to prevent one of the above outcomes.

AEs and SAEs. These will be monitored during colonoscopy; within 7 days; between 7 and 30 days. For each type of AE and SAE, rates of occurrence will be compared between treatment groups. Logistic regression will be performed to assess whether specific patient level characteristics are associated with any of the most frequently AEs or SAEs, such as cardiopulmonary events, bleeding, and so on.

Data security. All data will be de-identified and appropriate and applicable VA data security measures will be implemented.

Site performance. The data monitoring committee evaluates recruitment and retention performance monthly. Other performance problems such as protocol deviations, poor data quality, missing or overdue data, and reasons for withdrawal from study will be tracked. A monthly study conference call for study personnel including PD/PI, and all sites will be held to review study recruitment, data quality and protocol adherence. Study sites will be put on probation for poor performance, including under-recruitment. Typically, the probationary period is three months, at which time the site may be taken off probation, have probation continued or have funding stopped, depending on their performance during the probationary period.

